21.5.1 Bacteriuria

Bacteriuria will be considered as present if the urine culture indicates a single organism with a colony count >100,000 CFU and the subject is asymptomatic.

No treatment is required for asymptomatic bacteriuria and the subject may continue in the trial. Only the initial occurrence of bacteriuria should be reported on the Adverse Event eCRF. If the event persists with the same organism to the next visit, it would still be considered the same event. If bacteriuria with a new organism is present at a subsequent visit, it would be classified as a new event. If the bacteriuria converted to a symptomatic urinary tract infection, it would also be considered a new event (see below).

21.5.2 Symptomatic Urinary Tract Infection

The criterion below will be used to determine if a subject has a symptomatic UTI. The criterion is based on a publication from the Center for Disease Control⁴.

Symptomatic UTIs should be treated by the physician. If the physician determines that The Spanner should be removed as part of the treatment of a symptomatic UTI, the subject should continue in the study and attend the next study visit. Spanner devices removed for symptomatic UTIs need not be returned to the Sponsor.

Criterion for a symptomatic UTI:

Subject has at least **one** of the following signs or symptoms:

- • fever (>38°C)
- • suprapubic tenderness*
- • costovertebral angle pain or tenderness*

⁴ Urinary Tract Infection (Catheter-Associated Urinary Tract Infection [CAUTI] and Non-Catheter-Associated Urinary Tract Infection [UTI]) and Other Urinary System Infection [USI] Events, January 2015

- urinary frequency*
- urinary urgency*
- dysuria*

AND,

Subject has a urine culture with no more than two species of organisms, at least one of which is a bacteria of $\geq 100,000$ CFU/ml.

On a stent removal visit, if a subject has one of the above signs or symptoms **and** a positive urinalysis on that visit, the removal of stent is postponed as follows:

- Urine sample sent for Urine Culture and Sensitivity (as scheduled)
- The Subject will be scheduled for a follow-up visit to remove or replace the stent at a minimum of 72 hours after the initiation of treatment of the UTI.

*With no other recognized cause

21.5.3 Hematuria

Transient gross hematuria from the trauma of The Spanner insertion may occur during the follow up period. If this occurs, Spanner removal is not required but the incident should be reported as an Adverse Event.

If persistent gross hematuria or an event with significant frank bloody urine occurs in the follow up period, The Spanner should be removed. Cystoscopy should be performed as soon as possible and practical after removal of The Spanner to determine the source of bleeding and whether or not it is related to use of The Spanner. An Adverse Event should be recorded and the device returned to the Sponsor. The subject should continue in the study and attend the next study visit.

21.5.4 Pain or Perceived Bladder or Urethral Spasm

Severe pain. If a study subject experiences persistent severe pain believed to be related to The Spanner, it should be removed. Following removal of The Spanner, a cystoscopy should be performed as soon as possible and practical to determine whether trauma or injury to the urethra, bladder or bladder neck is the probable source of the pain. An Adverse Event should be recorded and the device returned to the Sponsor. The subject should continue in the study and attend the next study visit.

Moderate-mild pain or discomfort, perceived bladder or urethral spasm. The decision to remove The Spanner is left to the discretion of the subject and investigator. An Adverse Event should be recorded. If the device is removed due to the symptoms, it must be returned to the Sponsor. *Note: If the device is removed, the subject should continue in the study and attend the next study visit.*

21.5.5 Meatal Irritation and Discomfort

Meatal Irritation. Irritation is defined as an inflammatory response at the meatus. The decision to remove The Spanner is left to the discretion of the subject and investigator.

CONFIDENTIAL

An Adverse Event should be recorded. If the device is removed due to the symptoms, it must be returned to the Sponsor. *Note: If the device is removed, the subject should continue in the study and attend the next study visit.*

Meatal Discomfort. The decision to remove The Spanner is left to the discretion of the subject and investigator. An Adverse Event should be recorded. If the device is removed due to the symptoms, it must be returned to the Sponsor. *Note: If the device is removed, the subject should continue in the study and attend the next study visit.*

21.5.6 Migration or Expulsion of the Device

Migration- If migration of the Spanner is suspected, perform an x-ray or cystoscopy, if possible, to document the location of the device prior to attempting removal.

Subsequently, the device should be removed, either by locating and grasping the retrieval suture to remove the device or, if the retrieval suture cannot be located, by retrieving the device cystoscopically. In either case, care should be taken to assure that the proximal balloon is deflated prior to withdrawing the device through the urethra and that all of the device components are removed. (If possible, the balloon may be deflated by cystoscopically locating the suture that is attached to the proximal balloon and pulling it to remove the balloon drain plug to allow the balloon to empty. Alternately, the balloon may be ruptured cystoscopically using a cautery tool or wire guide.)

Record a Device Deficiency eCRF and return the device to the Sponsor. Provide a detailed description of any damage to the device that is known to have occurred as a result of removing the device (i.e. balloon punctured, suture between stent and distal anchor cut).

The subject should continue in the study and attend the next study visit.

Expulsion - Record a Device Deficiency eCRF and return the device to the Sponsor. Provide a detailed description of any damage to the device that is known to have occurred as a result of removing the device (i.e. balloon punctured, suture between stent and distal anchor cut). The subject should continue in the study and attend the next study visit.

Urinary Retention- If urinary retention occurs, and there is a question of whether the retention is related to bladder performance, an urodynamic evaluation should be considered to determine if bladder performance is contributing to urinary retention.

For urinary retention in a subject, cystoscopy or an x-ray should be performed prior to removal of The Spanner to verify whether device migration or inadequate stenting is the cause of the urinary retention. Subsequently, the device should be removed. After Spanner removal, the subject should be evaluated to determine voiding capability and urinary catheter bladder drainage instituted if needed.

An Adverse Event should be recorded and the device returned to the Sponsor. The subject should continue in the study and attend the next study visit.

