14.3 Primary Effectiveness Variable and Pass/Fail Criteria

The primary effectiveness endpoint is the success/failure of the subject to have a successful urinary void at all four study visits: (a) upon initial placement of the first stent (Visit 1), and (b) at all three visits in which the subject has a stent placed for 30 days (Visits 2, 3 and 4).

The primary effectiveness endpoint will be marked as a failure for a subject if any of the following occur:

- PVR of >150 ml at any visit (Visits 1, 2, 3, and 4)
- The subject withdraws from the trial

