14.6.3 Analysis of the Primary Effectiveness Variable

The following hypotheses will be tested at a one-sided $\alpha=0.025$ level of significance:

$$H_{a0}: p_s \leq 50\% \quad \text{vs.} \quad H_{a1}: p_s > 50\%$$

where p_s is the proportion of subjects with maintenance of successful voiding during the Spanner implantation period. This hypothesis will be tested using a one-sample exact binomial test. Summary statistics (counts and percentages) will be computed on the primary endpoint along with a 95% confidence interval on the treatment group success proportion.

² A major protocol deviation is defined as any protocol deviation that may affect the primary endpoint.

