21.2 AE Assessment, Documentation and Reporting

Complete an Adverse Event eCRF. Provide a complete description of the nature, severity and circumstances of the Adverse Event including results of physical examinations, diagnostic tests, treatments given, outcome of treatments and the subject's final condition.

Reports to the Sponsor.

Report all Serious Adverse Events, and Unanticipated Adverse Device Events to the Sponsor as soon as adequate information about the adverse event is available, but no later than 5 working days from the date the Investigator first became aware of the event. Notify the Sponsor by completing, or partially completing, Adverse Event eCRF.

Reports to the IRB.

Investigators are required to report all Unanticipated Adverse Device Events (See 21.3 for definition) to the reviewing IRB no later than 10 working days from the date that the Investigator first became aware of the event. In addition, the Investigator must comply with any other reporting requirements of the reviewing IRB.

21.3 Reporting Device Deficiencies.

If a device deficiency is suspected, The Spanner should be evaluated to determine if removal or replacement is necessary. All device deficiencies related to the identity, quality, durability, reliability, safety or performance of an investigational medical device shall be documented throughout the clinical investigation and appropriately managed by the sponsor. All Device Deficiencies, whether resulting in a symptom or not, should be reported as an Adverse Event and an Adverse Event eCRF should be completed.

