21.5 Managing Adverse Events and Device Deficiencies

CONFIDENTIAL

The following guidelines are recommended for managing Adverse Events and complications that may occur during the study. As these are only guidelines, the final decision for appropriate management of Adverse Events rests on the investigator's clinical judgment. Contact the SRS Medical for additional guidance on a case-by-case basis.

- If a device deficiency is known or suspected, The Spanner should be evaluated to determine if removal is necessary.
- If a device is removed in either in association with an adverse event or a device deficiency, then the subject is to attend the next scheduled visit.
- If the subject has no unresolved adverse events, then the subject should complete the study visit, including replacement of the stent and resume the study visit schedule.
- If the subject has unresolved adverse events, then complete as much of the study visit as possible, but do not place the stent. The subject should resume the study schedule and be reassessed at the next visit for the possibility of stent placement.

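### A man whose stent is removed for urinary retention between visits stays in the trial but is not a listed primary failure, and no rule scores his next visit when it has no on-stent PVR

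*Protocol*

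**What the plan says.** **Management of retention.** Under protocol 21.5.6 a man in retention has the stent removed. The text goes on: "After Spanner removal, the subject should be evaluated to determine voiding capability and urinary catheter bladder drainage instituted if needed". It then says: "The subject should continue in the study and attend the next study visit".

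**The next visit.** Protocol 21.5 gives two branches. If no adverse event is unresolved, "then the subject should complete the study visit, including replacement of the stent and resume the study visit schedule". If one is unresolved, the site is to "complete as much of the study visit as possible, but do not place the stent", and the man is reassessed one visit later. At Visits 2 and 3 (protocol 12.1.2 and 12.1.3) uroflow and PVR are listed before stent removal and placement of the next stent.

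**Primary endpoint.** Protocol 14.3 asks for a successful void at Visit 1 and "at all three visits in which the subject has a stent placed for 30 days". It lists two failures: a PVR above 150 ml at any of the four visits, and "The subject withdraws from the trial". SAP 4.2.1 adds failure to attend a scheduled visit. Protocol 8.3.1 and SAP 4.2.1 say PVR is assessed with the stent in place and define success by PVR at all four visits. Protocol 14.6.3 describes the parameter as "the proportion of subjects with maintenance of successful voiding during the Spanner implantation period".

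**Missing data.** SAP section 8 bases the primary presentation on observed data. Its worst-case analysis imputes failure when a visit is missed or the patient withdraws. Multiple imputation in protocol 14.11 covers missed visits, loss to follow-up and withdrawal.

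**Adjacent rule.** Protocol 21.5.8 requires withdrawal after two PVRs above 350 ml within a few hours.

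**The concern.** The trial tests the stent as an alternative to a urinary catheter. A man who loses the stent to retention and goes back to a catheter has not had that benefit, yet the plan keeps him in the study and has him attend. He has therefore neither withdrawn nor missed a visit. If he arrives without a stent, no on-stent PVR exists for that visit, and no rule says whether the visit is a failure, is missing, or can be rescued by a PVR taken off the stent or after re-stenting.

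This is an open-label, single-arm trial with one pass/fail criterion, so the choice should not be left until results are known. The event would still appear in the adverse event and Spanner removal tables (SAP 14.2 and 12.4), but those do not feed the primary proportion.

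**Working it through.** **1. Follow one man through the rules.** He has retention between Visits 1 and 2, the stent is removed, a catheter is placed, and two PVRs above 350 ml were not recorded.

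| Rule | Does it score him? |
|---|---|
| Protocol 14.3: PVR above 150 ml at a visit | Only if an off-stent PVR is taken, exceeds 150 ml and is counted |
| Protocol 14.3: withdrawal | No; 21.5.6 keeps him in |
| SAP 4.2.1: failure to attend | No; he attends |
| SAP section 8: observed data | Can leave him out of the denominator |
| SAP section 8: worst case | Worded for missed visits and withdrawals only |
| Protocol 14.11: multiple imputation | Same limits |

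The same unscored off-stent visit can follow removal for UTI, hematuria, pain or meatal irritation (21.5.2 to 21.5.5).

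**2. The plan's own figure.** Inputs from protocol 14.1 and SAP 5.3: 50% against 65%, 80% power, two-sided 5%. The normal approximation gives n = [(1.960 × 0.5 + 0.842 × √(0.65 × 0.35)) / 0.15]² = 84.8, rounded up to the stated 85 completers. The exact binomial test that the documents name needs 53 of 85 and has 73.6% power. That is a separate matter. The step below uses the ITT size of 105.

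**3. Pass marks at one-sided 0.025** (protocol 14.6.3, exact binomial, null 50%).

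- 105 men: 64 successes (p = 0.0157; 63 gives 0.0252).
- 104 men: 63 (p = 0.0195).
- 103 men: 62 (p = 0.0241).

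**4. Chance that j such men change the verdict.** Let X be the number of successes among 105 when these men count as failures. Assume each has PVR of 150 ml or less at his other visits.

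- Scored as successes instead, the verdict changes if 64 − j ≤ X ≤ 63.
- Dropped instead, it changes if X lies between the pass mark for 105 − j and 63.

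For j = 1 and j = 2 these are the same events: X = 63, and X = 62 or 63. At a true rate of 60%, P(X = 63) = 0.0793 and P(X = 62) = 0.0774, which sum to 0.1567.

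| True rate (such men as failures) | j = 1 | j = 2 |
|---|---|---|
| 55% | 4.6% | 10.2% |
| 60% | 7.9% | 15.7% |
| 65% | 4.5% | 8.1% |

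At the SAP's one-sided 95% bound the pass marks are 62/105, 61/104 and 61/103. At 60% the probabilities are 7.3% and 13.9% if scored as successes, and 7.3% and 7.3% if dropped.

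**5. False-pass rate.** Take a true rate of exactly 50% with these men as failures, and assume a share q of men are such cases. The chance of passing at one-sided 0.025 is 1.6% if they are scored as failures. For q = 1% or 2% it is 2.6% or 4.1% if they are scored as successes, and 2.4% or 3.3% if they are dropped.

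**The case against.** **Success is already defined.** The success wording requires a qualifying PVR at all four visits, measured with the stent in place, and 14.3 speaks of visits after 30 days of stent use. A reader might infer from the gap that the plan counts men back on a catheter as successes. The documents do not support that: a strict analyst would refuse it. What stands is that no sentence turns this refusal into a failure, while SAP section 8 offers exclusion as an alternative.

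**The denominator problem is wider.** SAP section 8 conflicts with SAP 4.2.1 for all missing data, and ITT is the primary set. Resolving that conflict would remove much of the exclusion route. It would still not score this man unless the wording reached attended visits without an on-stent PVR. Whether attending without a PVR counts as missing an evaluation visit is arguable.

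**The case is narrow.** Two PVRs above 350 ml lead to withdrawal, a listed failure. Entry requires retention, so an off-stent PVR may well exceed 150 ml and fail him if counted. Both points reduce the frequency without closing the gap.

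**Early replacement.** A reader might also infer that replacing a migrated or occluded stent before the visit hides a failure. Protocol 21.3 says only that "The Spanner should be evaluated to determine if removal or replacement is necessary", with no timing, and 21.5 puts re-stenting at the next scheduled visit. A man with on-stent PVR of 150 ml or less at all four visits meets the endpoint as written. Failing him for early replacement alone would change the endpoint.

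**Conclusion.** The concern holds as an unscored case rather than as a rule that rewards failure. A man whose stent is removed for retention, without the two high PVRs, continues and attends, is not a listed failure, can be dropped under the observed-data presentation, and falls outside the wording of the worst-case analysis. Compared with scoring him as a failure, every route open to the analyst can only raise the primary proportion.

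The size is illustrative. The documents give no retention rate, so counts of one or two men are assumptions, as is a PVR within the limit at those men's other visits. The 60% example lies close to the pass mark of 64/105 = 61%, where sensitivity is high. The handling of such men matters only if the result is close. It is worth fixing because the fix is cheap.

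**What to change.** Add to protocol 14.3 and SAP 4.2.1:

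1. *At Visits 2–4 only a PVR taken with the stent in place, before its removal, can count as a success. A visit attended without such a PVR is scored as a failure, and the subject stays in the ITT denominator in the primary analysis.*
2. *Stent removal for urinary retention followed by catheter drainage between Visit 1 and Visit 4 is a primary failure, even if the subject continues in the study.*

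Apply both rules to the secondary PVR endpoints over their own visits: through Visit 2 for the two 30-day endpoints and through Visit 4 for the 90-day 250 ml endpoint. Do not add automatic failure for early replacement of a migrated or occluded stent when on-stent PVR is 150 ml or less at all four visits.

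**Cost.** The change is wording only. Removals and post-Spanner drainage are already tabulated (SAP 12.4 and 12.5), so new data collection should not be needed. The real downside is that a man off the stent at a visit for UTI, hematuria, pain or meatal irritation also fails. That is consistent with how SAP 4.2.1 treats missed visits and withdrawals, but the success rate may be slightly lower. A sensitivity analysis can show the result without those men counted as failures.

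To gauge the cost: if 65% applied to all 105 men and counted such men as successes, moving one or two to failure would lower power at the 64 mark from 83.5% to 77.8% or 71.3%. The plan attaches 65% to the 85 completers, so 83.5% is not the plan's power and these figures show sensitivity only.

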21.5.7 Occlusion of the Device Drainage Lumen or Device Malfunction

If occlusion or malfunction of the device is suspected, The Spanner should be removed. A Device Deficiency eCRF should be completed and the device returned to the Sponsor. The subject should continue in the study and attend the next study visit.

21.5.8 Criteria for Spanner Removal and Re-establishment of Bladder Drainage: Clinically Significant Post Void Residual Urine

For purposes of the clinical trial, PVR > 350 ml on two measurements taken within a few hours will be considered as significant and requiring intervention. If the subject has a PVR > 350 ml on two measurements taken within a few hours at any scheduled or visit, or at other medical visit, the intervention should include the removal of The Spanner, the re-establishment of bladder drainage (CIC or Foley) and the premature withdrawal of the subject from the study.

22 VULNERABLE POPULATION

This study will not recruit nor enroll subjects from vulnerable populations nor under emergency conditions.

23 SUSPENSION OR PREMATURE TERMINATION OF THE CLINICAL INVESTIGATION

23.1 Procedure for Suspension or Premature Termination

The sponsor may suspend or prematurely terminate either a clinical investigation in an individual investigation site or the entire clinical investigation for significant and documented reasons. A principal investigator, IRB, or regulatory authority may suspend or prematurely terminate participation in a clinical investigation at the investigation sites for which they are responsible. If suspicion of an unacceptable risk to subjects arises during the clinical investigation, or when so instructed by the IRB or regulatory authorities, the sponsor shall suspend the clinical investigation while the risk is assessed. The sponsor shall terminate the clinical investigation if an unacceptable risk is confirmed.

The sponsor shall consider terminating or suspending the participation of a particular investigation site or investigator in the clinical investigation if monitoring or auditing identifies serious or repeated deviations on the part of an investigator.

CONFIDENTIAL

If suspension or premature termination occurs, the sponsor shall justify its decision in writing and promptly inform the other parties with whom they are in direct communication. The principal investigator and sponsor shall keep each other informed of any communication received from either the IRB or the regulatory authority.

If, for any reason, the sponsor suspends or prematurely terminates the investigation at an individual investigation site, the sponsor shall inform the responsible regulatory authority as appropriate and ensure that the IRB is notified, either by the principal investigator or by the sponsor. If the suspension or premature termination was in the interest of safety, the sponsor shall inform all other principal investigators.

If suspension or premature termination occurs,

- a) the sponsor shall remain responsible for providing resources to fulfil the obligations from the CIP and existing agreements for following up the subjects enrolled in the clinical investigation, and
- b) the principal investigator or authorized designee shall promptly inform the enrolled subjects at his/her investigation site, if appropriate. The method and the timing of this communication will depend on the circumstances and the perceived risks. All subjects must have the device removed and attend a 1 month follow-up visit.
- c) the study is not blinded so there need not be criteria for breaking the blind.

